Upload copy(ies) of bolded Consent Form(s)

Upload copy(ies) of recruitment materials/ads to be reviewed

Upload copy(ies) of the HIPAA form

HIPAA Waiver-alteration of consent_2020-04-21_CB.pdf

HIPAA consent_2020-04-24.pdf

Upload any additional documents that may be related to this study

Post_Study_Feedback_Questionnaire_4.6.2021.pdf

Statistician	Data preparation and analysis is performed by a research scientist for the team.
Study Objectives	
The primary purpose of this study is to determine whether heightened anxiety in the context of COVID-19 can be reduced through web-based interventions.
 
This randomized clinical on-line study will examine whether a daily practice of meditation or Kundalini Yoga with anxiety reduction training leads to a greater reduction in anxiety than anxiety reduction training alone.

Primary endpoint	Week 8 evaluation.
Study Design	
This randomized on-line study is for individuals with anxiety and distress triggered by COVID-19 who have not yet been infected with the novel corona virus.
 
The primary study goal is to examine the extent to which anxiety can be reduced through the use of on-line training programs. All participants will receive Anxiety Reduction Training using cognitive-behavioral methods known to be helpful in reducing stress, anxiety, depression, and insomnia. In addition, two-thirds of participants will be randomly assigned to receive training in either Kundalini Yoga (KY) or mindfulness meditation. The investigators will assess the degree to which each of these training programs lead to reduced stress, improved well-being, decreased multisystem symptoms, enhanced mood, and reduced cognitive complaints. Participants will complete self-report assessments at 2-week intervals during the 8 weeks of the acute phase of the study and then again 3- and 6-months later. For details see PSF.

General Study Population	See PSF respective section
Inclusion-Exclusion Criteria	See PSF respective section
Study Assessments	See PSF respective section
Sample size	The study enrollment was closed in 2022 with a sample size of 256.
Randomization	Randomization will be a simple allocation with 1:1:1 ratio. Participants will be randomly assigned to one of three groups: a) Meditation (using Journey meditation) with psychoeducation; b) Kundalini Yoga (provided through an on- line video program) with psychoeducation; or c) psychoeducation alone.
Primary aim#1	Aim 1: Test whether Kundalini Yoga with psychoeducation results in a significantly greater reduction in anxiety and multi-system symptom severity compared to psychoeducation alone.
Primary aim #2	Aim 2: Test whether a mindfulness meditation practice with psychoeducation leads to a significantly greater reduction in anxiety and multi-system symptom severity compared to psychoeducation alone.
Secondary aims and Exploratory goals:	
Aim 3: To assess whether treatment outcomes are moderated by COVID-19 related variables and personal variables.
 
Aim 4: To assess at the follow-up at month 3 whether patients have continued with the meditation practice and whether gains observed at week 8 have been sustained.
 
Aim 5: To assess whether there is a difference in both primary and secondary outcomes between the Kundalini Yoga and the meditation treatment groups.

Timing of Analysis	Analysis will be performed after the study is stopped for enrollment and a year after to make sure that all participants have finished their participation.
Analysis Population	We conduct analysis of a change score between baseline and week 8 for those who were randomized into one of the study arms and completed active treatment phase.
Missing Data	Missing data is treated as missing at random
Interim Analyses and Data Monitoring	There is no interim analysis for the protocol.
Primary aim#1 analysis	To investigate whether Kundalini Yoga with psychoeducation results in a significantly greater reduction in two primary outcome measures compared to psychoeducation alone, we will compare two groups of completers using one-sided t-test. P-value and estimation parameter value will be provided.
Primary aim#2 analysis	To investigate whether mindfulness meditation practice with psychoeducation leads to a significantly greater reduction in two primary outcome measures compared to psychoeducation alone, we will compare two groups of completers using one-sided t-test. P-value and estimation parameter value will be provided.

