Protocol Title:
**Meditation and Yoga for Heightened Anxiety
related to COVID-19**

Version Date:
12/19/2023

Protocol Number:
7987

First Approval:
04/27/2020

Research Area:
Anxiety, Mood, Eating & Related Disorders

Expiration Date:
No Expiration

Division:
Anxiety/PTSD/OCD

Contact Principal Investigator:
[name]
Email: **[contact]**
[contact]**

Co-Investigator(s):
[name]

Research Chief:
[name]

Annual Progress

Current Status of Study

Current Status of Study

Only data analysis is ongoing

Number of participants currently enrolled:

0

Is NYSPI-IRB the IRB of record? If No, specify the IRB of record and, if applicable, provide a copy of the most recent approval notice.

Yes

Confirmations:

- ✓ Confirm there have been no un-reported serious adverse events (SAEs)
- ✓ Confirm there have been no unapproved modifications

Total Number of participants enrolled to date:

256

Summary

Have there been any study findings, recent literature, or untoward events occurring here or at other sites in the past year which might affect the analysis of the safety, risks or benefits of study participation?

No

Confirm that all study staff with a significant role in the design or implementation of the human subject components of this study has completed required training in human research subject protections.

✓ Yes

Overall Progress

Approved sample size:

450

Total number of participants enrolled to date:

256

Number of participants who have completed the study to date:

256

Has the drop-out/withdrawal rate been significant?

Yes

There was sizeable dropout by week 2. Of the 256 who were randomized, by the end of the first two weeks, the drop-out rate was 49% for psychoeducation alone, 52% for psychoeducation plus meditation, and 69% for psychoeducation and Kundalini yoga (calculated based on the number of participants who completed at least one questionnaire by the end of the week 2). By the end of the treatment period in the study (week 8) the drop-out was 71% for psychoeducation alone, 72% for psychoeducation plus meditation, and 84% for psychoeducation and Kundalini yoga.

Comments / Additional Information

N/A

Procedures

To create the protocol summary form, first indicate if this research will include any of the following procedures

- ✓ Somatic Treatment or Intervention
- ✓ Internet-based Data Collection or Transmission

Population

Indicate which of the following populations will be included in this research

- ✓ Medically Ill Subjects
- ✓ Adults

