If deemed eligible based on the answers related to I/E criteria, participants will be notified to complete informed consent on Proofpilot's website. Individuals who have questions about the study can email the study coordinator. Once consent is completed, they will then be asked to watch a video to encourage their full participation throughout the 8 weeks. They will then complete the baseline set of assessments prior to randomization.

If deemed ineligible to participate, participants will be encouraged to identify a yoga or meditation group in their community. If deemed ineligible due to suspected COVID-19 symptoms, patients will be advised to contact their local health care provider. Patients who score in the severe range for depression and who are excluded from participation will be advised to contact a local health provider for further evaluation of depression.

Study Procedure

Outcome Measures and other assessments. All participants will complete the baseline self-report questionnaires which assess current symptoms, impact of COVID-19, and additional medical and psychosocial history (including lifetime stressors). The full battery of Primary and Secondary outcome measure battery and COVID Follow-up queries will be conducted at baseline, and weeks 4, 8 (primary outcome), and at 3- and 6-months post-treatment. On a biweekly basis to week 8 (primary outcome time point), patients will complete the primary outcome measures and will be asked about their health status and any change in medication or treatment. In addition, on a daily basis, patients randomized to meditation or Kundalini Yoga will be asked to complete a daily log of their daily meditation/yoga practice.

1. Primary Outcome Measures

1. Symptom-based measures. GAD-7 (generalized anxiety); Whiteley-8 (health anxiety)

Secondary Outcome Measures

1. Symptom-based measures:

- PROMIS sleep disturbance
- PHQ8 (depression)
- SSS-8 (somatic symptoms)
- ERQ (emotion regulation)
- PSS-10 (stress)
- Brief hypervigilance scale

2. Health status: Overall Health in general (1 item)

3. Cognition: Neuro-QOL - Applied Cognition (8 items)

Moderators

Selected demographic variables

COVID-19 Exposure and related variables (“CRISIS” survey)

Intolerance of Uncertainty

Mental Health History

Prior Experience with Mind-body practices

Personal Religiosity or Spirituality (Importance; Identification)

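### The primary test is an unadjusted t-test on change from baseline, although a pre-randomisation baseline of each primary measure is available as a covariate and the groups are small

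*Combined protocol and SAP*

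**What the plan says.** The Analysis Population row of the SAP table reads "We conduct analysis of a change score between baseline and week 8", restricted to those who finished the active treatment phase. Both primary-aim rows add that "we will compare two groups of completers using one-sided t-test". Neither row names a covariate, and no regression or mixed model appears elsewhere. The only adjustment mentioned (Lay Summary; Research Related Delay to Treatment) concerns therapies taken after week 8, which is a different question. The Missing Data row says "Missing data is treated as missing at random".

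The Primary Outcome Measures list names GAD-7 and Whiteley-8, and the Assessment Instruments table schedules both at baseline and weeks 2, 4, 6 and 8. On timing, the Consent Procedures part of Study Procedures says of consented participants: "They will then complete the baseline set of assessments prior to randomization". On allocation, the SAP says: "Randomization will be a simple allocation with 1:1:1 ratio". Overall Progress gives week-8 drop-out as "71% for psychoeducation alone, 72% for psychoeducation plus meditation, and 84% for psychoeducation and Kundalini yoga".

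**The concern.** A change score assumes that one point of baseline difference carries through as one point at week 8. In a population selected for high anxiety, some regression to the mean is expected, so the true slope may well be below 1. Fixing it at 1 has two consequences. The outcome keeps baseline noise that an estimated slope would remove. And an arm that happens to start worse shows more improvement even when treatment does nothing.

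Simple allocation does nothing to limit baseline differences, and heavy drop-out leaves few people to average them out. With a one-sided test, a chance imbalance in one direction looks like benefit, and in the other it hides benefit. The covariate that would deal with this is already collected.

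**Working it through.** **Plan's own figures.** There is nothing to reproduce on this point: the documents state no effect size, SD, alpha, power or baseline-to-week-8 correlation. All inputs below other than 256 randomised and the drop-out rates are assumptions, shown as ranges.

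**Group sizes.** 256 / 3 is about 85 per arm; actual arm sizes are not given, so 75 to 95 is used. Week-8 completers:
- psychoeducation: 75–95 × 0.29 = 22–28
- meditation: 75–95 × 0.28 = 21–27
- yoga: 75–95 × 0.16 = 12–15

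The calculations take 14 yoga versus 25 psychoeducation (N = 39) and an assumed one-sided 5% level.

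**Precision.** Set the week-8 SD to 1. Let r be the baseline-to-week-8 correlation and k the baseline SD divided by the week-8 SD.
- Change-score variance: 1 + k² − 2rk
- Residual variance after adjustment (ANCOVA): 1 − r²
- Small-sample penalty for estimating the slope: variance × (N − 3)/(N − 4) = 36/35, and a t quantile on 36 rather than 37 degrees of freedom

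| k | r | Change variance | Adjusted variance | Ratio | Interval width before penalty | After penalty |
|---|---|---|---|---|---|---|
| 1 | 0.3 | 1.40 | 0.91 | 0.650 | 19% narrower | 18% narrower |
| 1 | 0.5 | 1.00 | 0.75 | 0.750 | 13% narrower | 12% narrower |
| 1 | 0.7 | 0.60 | 0.51 | 0.850 | 8% narrower | 6% narrower |
| 0.8 | 0.3 | 1.16 | 0.91 | 0.784 | 11% narrower | 10% narrower |
| 0.8 | 0.5 | 0.84 | 0.75 | 0.893 | 6% narrower | 4% narrower |
| 0.8 | 0.7 | 0.52 | 0.51 | 0.981 | 1% narrower | 0.5% wider |
| 0.7 | 0.3 | 1.07 | 0.91 | 0.850 | 8% narrower | 6% narrower |
| 0.7 | 0.5 | 0.79 | 0.75 | 0.949 | 3% narrower | 1% narrower |
| 0.7 | 0.7 | 0.51 | 0.51 | 1.000 | no change | 1.5% wider |

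**Detectable effect** at 80% power (noncentral t, penalty included, r = 0.5, in week-8 SDs), change score to adjusted: 0.85 to 0.74 (k = 1), 0.78 to 0.74 (k = 0.8), 0.75 to 0.74 (k = 0.7).

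**Baseline imbalance.** The standard error of a chance baseline difference is √(1/14 + 1/25) = 0.33 baseline SD, so 0.3 SD is about 0.9 standard errors. A difference at least that large, in either direction, arises by chance in about 37% of trials. It shifts the change-score contrast by 0.3(k − r): at r = 0.5 that is 0.15, 0.09 and 0.06 week-8 SD for k = 1, 0.8 and 0.7.

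Simulation (100,000 bivariate-normal trials per cell, no treatment effect, no informative drop-out) gives these rejection rates for the nominal 5% change-score test:
- yoga 0.3 SD higher (worse) at baseline: 7–8% at r = 0.3–0.5; 5–8% at r = 0.7
- yoga 0.3 SD lower at baseline: 0.4–3% at r = 0.3–0.5
- adjusted test, in either case: about 5%
- both tests, averaged over all randomisations: about 5%

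**The case against.** The strongest reply is that the planned test is valid: over repeated randomisations, with no differential loss, its error rate is 5%. That stands. The criticism concerns precision and accuracy given the baseline difference actually seen.

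Second, the gain may be slight. Entry requires a GAD-7 of 7 or more, which plausibly compresses the baseline spread and pushes k below 1. At k = 0.7–0.8 and r = 0.5–0.7, the intervals range from 4% narrower to 1.5% wider. This stands for GAD-7. Whiteley-8 has no entry cut-off, so the argument does not carry over to it directly.

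Third, unequal loss among completers is the larger problem, and adjusting completers does not cure it. True; this is why the adjustment belongs in a model of everyone randomised. The benefit of that model is not quantified here. The figures above compare two completers-only analyses under normality without informative drop-out.

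Fourth, the aims name multi-system symptom severity as the second primary outcome. If that means SSS-8, it is scheduled only at baseline and weeks 4 and 8 within the treatment phase, so a model using weeks 2 and 6 would not be possible for it. However, the protocol's itemised list gives exactly two primary measures, matching the SAP's reference to two. Baseline adjustment of the week-8 score works on either reading.

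Finally, changing a primary analysis after data collection has a credibility cost. That is real and must be handled openly.

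**Conclusion.** The concern holds. It is a loss of efficiency and of conditional accuracy, not an invalid test, and it should be corrected. The trade-off is lopsided: at 14 versus 25, the best case examined is an interval 18% narrower (k = 1, r = 0.3) and the worst 1.5% wider (k = r = 0.7). For GAD-7 the smaller gains are the more plausible. Protection against a misleading one-sided p-value after an ordinary baseline imbalance matters at least as much. These sizes rest on assumed arm sizes, r, k and alpha; that the plan makes no baseline adjustment does not.

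**What to change.** **Preferred.** For each primary measure, fit a repeated-measures model to the week 2, 4, 6 and 8 scores of all randomised participants, with arm, week, arm-by-week and that measure's baseline. Use the score taken after consent and before randomisation; GAD-7 is also collected at screening, so the SAP should say which is meant. Alternatively, enter baseline as a response with a common mean across arms, which keeps everyone with a baseline score. Apply a small-sample degrees-of-freedom correction and report the week-8 adjusted mean difference of each active arm versus psychoeducation with its 95% confidence interval. Unlike a completers-only t-test, this makes use of the SAP's missing-at-random assumption.

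It would also draw on earlier data. By week 2, "the drop-out rate was 49% for psychoeducation alone, 52% for psychoeducation plus meditation, and 69% for psychoeducation and Kundalini yoga". Retained at week 2 over retained at week 8 is therefore 0.51/0.29 = 1.8 (psychoeducation), 0.48/0.28 = 1.7 (meditation) and 0.31/0.16 = 1.9 (yoga), whatever the arm sizes. The week-2 figure counts anyone with at least one questionnaire, so usable primary-outcome data may be fewer. If SSS-8 is declared primary, its model uses weeks 4 and 8.

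**Minimum.** Replace each t-test by a regression of the week-8 score on arm and that measure's baseline, and state that in completers this does not correct for unequal drop-out.

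**Either way,** record a dated SAP change with its reason, say whether week-8 outcomes by arm had been seen, and report the planned t-test alongside.

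**Cost.** No new data for GAD-7 or Whiteley-8. The covariate takes one degree of freedom; in the worst case examined, intervals are about 1.5% wider (1.8% at 12 versus 22). The repeated-measures model also estimates arm-by-week and covariance terms, with perhaps 12–15 yoga participants left at week 8. Because only analysis remains and drop-out by arm is known, the main cost is the need for an open, justified amendment.

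### Both primary tests use completers only (about 62 of 256 if arms are equal), which the SAP's missing-at-random assumption does not justify; the yoga comparison is most exposed

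*Combined protocol and SAP*

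**What the plan says.** The Analysis Population row of the SAP takes the change from baseline to week 8 "for those who were randomized into one of the study arms and completed active treatment phase". The Missing Data row reads in full: "Missing data is treated as missing at random". Both primary-aim analysis rows say "we will compare two groups of completers using one-sided t-test". Nowhere does the combined document name a covariate, imputation, weighting, a likelihood model, an all-randomised analysis set or a sensitivity analysis.

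Two things that any analysis needs are also unsettled.

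- **The measures.** SAP Aim 1 asks whether yoga with psychoeducation "results in a significantly greater reduction in anxiety and multi-system symptom severity compared to psychoeducation alone". Its analysis row tests for a "significantly greater reduction in two primary outcome measures compared to psychoeducation alone" and does not name the two. Study Procedures lists GAD-7 and Whiteley-8 as primary and places SSS-8, the likeliest candidate for multi-system symptoms, among the secondary measures. The schedule has GAD-7 and Whiteley-8 at baseline and weeks 2, 4, 6 and 8. SSS-8 is taken only at baseline and weeks 4 and 8 during treatment.
- **Completion.** The SAP does not define it. Overall Progress ties its week-2 dropout rate to having returned at least one questionnaire by then and attaches no rule to week 8. It also enters 256 as having completed, which may be an administrative count.

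**The concern.** Dropout that depends on arm alone would not bias the completer contrast. MAR allows more than that: leaving may depend on scores already observed, and those scores are correlated with later change. The completer t-test uses none of the data from people who left, so MAR by itself does not make it valid. The stated assumption and the stated method do not match.

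The hypothesis concerns people with heightened anxiety, not those who finish eight weeks. About three quarters of those randomised are left out by an event after randomisation. For yoga that event is more frequent than in control, so the estimated benefit of adding yoga can be mixed with who stayed. The documents give no scores or dropout reasons by dropout status, so neither the size nor the sign of the bias can be known from them.

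**Working it through.** **Inputs.** 256 randomised (SAP, Sample size), by simple 1:1:1 allocation (SAP, Randomization). Arm sizes are not given; 256/3 = 85.3 is assumed, with a range of 71-100. Dropout for psychoeducation, meditation and yoga: 49%, 52%, 69% by week 2 and 71%, 72%, 84% by week 8 (Overall Progress). Required completers 270 and enrolment 360 (Description of Subject Population). No alpha, effect size, SD or correlation is stated; one-sided 5% is assumed.

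**1. The plan's own figure.** The 270 cannot be derived without alpha, power, effect size and SD. It agrees with 360 at 25% loss (270/0.75 = 360). With the 450 given elsewhere, the implied loss is 1 - 270/450 = 40%. Actual loss was 71-84%.

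**2. Who is analysed.** A completer is taken as anyone not counted as a week-8 dropout.

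| Arm | By week 2 | At week 8 |
|---|---|---|
| Psychoeducation | 85.3 x 0.51 = 43.5 | 85.3 x 0.29 = 24.7 |
| Meditation | 85.3 x 0.48 = 41.0 | 85.3 x 0.28 = 23.9 |
| Yoga | 85.3 x 0.31 = 26.5 | 85.3 x 0.16 = 13.7 |
| Total | 110.9 | 62.3 |

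62.3/256 = 24%, and 62.3/270 = 23%. Over arm sizes of 71-100 the total is 60-64. Of the 256 - 62.3 = 193.7 left out, 110.9 - 62.3 = 48.6 had returned a questionnaire by week 2. For SSS-8, interpolating retention to week 4 gives 94.7 - 62.3 = 32.4 (possible range 0-49).

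**3. Is loss different by arm?** Fisher tests on rounded counts:

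- Yoga v control, week 2: 26/85 v 44/86, p = 0.008 (0.005-0.023 over arm sizes 71-100).
- Yoga v control, week 8: 14/85 v 25/85, p = 0.067 (0.030-0.099).
- Meditation v control: about 0.8 and 1.0.

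**4. Why MAR is not enough.** Let D be the change and R completion. The t-test estimates the arm difference in E[D | R = 1]. This equals the randomised difference in E[D] only if the shift E[D | R = 1] - E[D] is the same in both arms. Under MAR the shift depends on how much is lost and on how strongly loss follows earlier scores. In Aim 1 the amounts differ, so the shifts differ even with one common mechanism. In Aim 2 the amounts are nearly equal, so the shifts nearly cancel unless the mechanisms differ.

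**5. Illustrative size.** Simulation with no true effect: five visits, unit SD, AR(1), and dropout depending on the last seen score, calibrated to the stated week-2 and week-8 rates. Slopes (log-odds per SD) and correlations are assumed. Absolute bias of the Aim 1 completer contrast, in SD, by baseline-week 8 correlation:

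| Score-dependent dropout | Slope | 0.316 | 0.5 | 0.7 |
|---|---|---|---|---|
| Same in both arms | 0.35 | 0.045-0.046 | 0.028-0.036 | 0.020 |
| Same in both arms | 0.7 | 0.081-0.083 | 0.059-0.060 | 0.036-0.037 |
| One arm only | 0.35 | 0.105-0.151 | 0.077-0.110 | 0.045-0.067 |
| One arm only | 0.7 | 0.184-0.268 | 0.123-0.193 | 0.076-0.115 |

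The same-mechanism bias is 8-21% of the contrast's own sampling SD (0.26-0.41), with one-sided rejection of 3-7%. With one arm only, rejection is 1-15%. For Aim 2 the bias is at most 0.02 SD with the same mechanism and 0.05-0.20 SD with one arm only. A second simulation, with slopes from -0.5 to 1, gave 0.03-0.10 SD (same) and 0.09-0.29 SD (differing) for Aim 1. Adding baseline as a covariate among completers still left about 0.06-0.20 SD when mechanisms differed by arm.

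**6. The alternative under the same conditions.** A likelihood model on all visits was off by at most 0.01 SD, but only because dropout was generated as MAR. On the SSS-8 schedule it left at most 0.02 SD (same) or 0.02-0.08 SD (one arm) when dropout followed scores at visits where SSS-8 is not taken. When dropout followed the unseen current score, the all-visits model was off by 0.01-0.05 SD (same) or 0.05-0.22 SD (one arm), and the completer contrast by under 0.04 SD.

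**The case against.** The best defence has four parts.

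- **Size.** If dropout works alike in both arms, the bias is small beside sampling error. The larger figures need score-dependent dropout in one arm only, which no section documents for either aim. All slopes and correlations are assumed.
- **The remedy may be no better.** If dropout follows unseen scores, the proposed model did worse than the completer test in step 6.
- **Timing.** Enrolment closed in 2022 and only analysis remains, so replacing the primary analysis now could be data-driven.
- **Visible intent.** The protocol counted required completers, so a completer focus was not hidden.

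Much of this stands. Bias is shown to be possible, not to have occurred, and the model is not shown to be more accurate if MAR fails. The small completer error in that run, however, comes largely from baseline and week-8 selection cancelling in a stationary set-up, so it does not vindicate the t-test. The argument also cuts against resting Aim 2 on near-equal loss, which does not protect it if reasons for leaving differ.

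It does not rescue the plan as written. The SAP chose MAR, its method does not follow from MAR, and nothing supports the result from another angle. Counting required completers does not make the completer contrast a randomised one.

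It is also fair to ask whether the roughly 49 excluded people really have outcome scores. Baseline forms precede randomisation and GAD-7 and Whiteley-8 are due at week 2, so this is a reasonable inference. Overall Progress does not say which questionnaire was returned. The other 145 or so (193.7 - 48.6) would contribute baseline only.

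**Conclusion.** The point holds and should be resolved before results are reported. Both primary tests use about 24% of those randomised, and the SAP's own missing-data assumption does not make them valid. The risk lies chiefly in Aim 1, where loss is 84% v 71% at week 8. Aim 2 has balanced but very heavy loss and would be materially biased only if the mechanism differed between arms.

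The count of 62 assumes equal arms and that completer means not a week-8 dropout. The bias sizes are illustrations under assumed slopes and correlations. The case for change rests on the mismatch between assumption and method, the amount of loss and the absence of any supporting analysis, not on one simulated value. No single analysis is safe at this level of loss.

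**What to change.** 1. Reconcile Study Procedures with the aims and name the two primary measures in the SAP.
2. Analysis Population: all randomised participants, analysed as randomised.
3. Primary analysis, for each measure: a likelihood-based repeated-measures model on its scheduled visits to week 8 (baseline and weeks 2, 4, 6, 8 for GAD-7 and Whiteley-8; baseline and weeks 4 and 8 for SSS-8 if it is primary). Use arm by time, a common baseline mean, unstructured covariance with a pre-specified simpler fallback, and a small-sample degrees-of-freedom correction such as Kenward-Roger, since only about 14 yoga participants reach week 8. The contrasts are the week-8 differences from psychoeducation. Confirm the visits actually held, because the Lay Summary and Background describe weekly assessments while the schedule is two-weekly.
4. Define completer, reconcile it with the entry of 256 completed, and keep the completer t-test as a labelled supplementary analysis.
5. Add delta-adjusted sensitivity analyses with arm-specific deltas, since MAR cannot be tested.
6. Map any discontinuation assessments obtained to visits. Report baseline scores, last scores and dropout reasons by arm and dropout status.
7. Date the change, state whether outcomes had been seen, and report both analyses side by side.

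**Cost.** No new data are needed, only programming. The estimate leans on MAR for those with baseline only. The main cost is a late, disclosed change to the primary analysis. The precision gain is modest: against baseline-adjusted completers, the simulated Aim 1 standard error falls by about 5-13% with all visits and 2-9% on the SSS-8 schedule.
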